9.2.3 Exploratory Objectives

To assess the effect of sargramostim treatment, as compared to placebo, on clinical progression of in individuals with mild-to-moderate AD.

Well validated neuropsychological assessments will be administered and scored using the standardized scoring methods associated with each of the neuropsychological tests. Analysis of the change in cognition from Baseline to EOT will be measured by the change in scores for the MoCA, ADAS-cog₁₃ total scores, CDR-SB, TMT A, ADCS-ADL score, measures of verbal fluency (lexical and semantic) and the NPI score. Due to the multitude of both the neuropsychological tests and the different time points that these tests are administered, a correction method will be used to counteract the problem of multiple comparisons.

To assess the effect of sargramostim treatment, as compared to placebo, on metabolic activity in different brain regions in individuals with mild-to-moderate AD.

FDG-PET will be used to assess overall metabolic activity in different brain regions, particularly in the medial temporal lobe in potential correlation with changes in MTA, at baseline and at EOT. Standard protocols for 18F-FDG PET imaging studies in conjunction with amyloid PET imaging studies, will be used ^{125, 126}.

To assess the effect of sargramostim treatment, as compared to placebo, on brain amyloid deposition in individuals with mild-to-moderate AD.

CSF assay may be performed examining $A\beta(1-42)$ and t-tau: $A\beta$ (1-42) ratio. The assay will be conducted during of screening and at the End of Treatment). Additionally, there will be an option utilizing Amyloid PET scans, performed using Vizamyl, produced at the CU-AMC / Pharmalogic cyclotron laboratory, which allows for amyloid-beta neuritic plaque density imaging. The Amyloid PET scans may be performed at Screening Visit and at the Follow-up Visit. Vizamyl is approved by the FDA for use in research and clinical application. For this protocol, the change from the screening scan's standardized uptake value ratio (SUVR) to follow-up SUVR will be similarly analyzed by a contracted central reading facility, using the participant's MRI to reduce white matter contamination, thereby increasing the SUVR signal change by eliminating counts in the region that do not change (i.e. white matter). The PET scans and accompanying MRI scans will be stripped of any personal identifying information, containing only the trial's randomized subject ID number and date. The results of the PET quantitative analyses will not be used to make any treatment decisions.

To assess the effect of sargramostim treatment, as compared to placebo, on AD related changes in peripheral blood and CSF biomarkers in individuals with mild-to-moderate AD.

Levels of AD-associated biomarkers in peripheral blood samples (collected at Baseline, 12, EOT and follow-up) and CSF samples (collected at Screening Visit and EOT) will be compared between placebo

controls and sargramostim treatment groups. The identification of circulating biomarkers in AD is a relatively new field, with inconsistent biomarker level results reported as increased, decreased, or unchanged between studies ¹²⁷. These mixed results mean that standardized levels for AD-associated circulating biomarkers have yet to be established. Therefore, we will compare observed biomarker levels from our project to other published levels to explore whether any similarities are observed. This comparison, as well as our own results, will add to the AD-associated blood and CSF biomarker fields of literature.

To assess the effect that ApoE genotype may have upon predicting sargramostim treatment outcomes in individuals with mild-to-moderate AD.

ApoE genotyping will be performed using blood samples collected on Day 1 of this trial for each participant. ApoE genotype will be determined either by Athena Diagnostics, or in the University of Colorado laboratory under the direction of [name], using established methods. Outcomes in the context of ApoE genotype will be compared. The genetic testing will be carried out at the end of the trial, and participants will not be notified of any genetic testing results.

To assess the effect of sargramostim treatment, as compared to placebo, on inhibiting MTA in individuals with mild-to-moderate AD.

MTA will be assessed using an automated rating system to grade the severity of atrophy in the entire medial temporal region will be employed using the FreeSurfer software automated rating system of individual medial temporal structures, i.e., the hippocampus (HPC), entorhinal cortex (ERC) and perirhinal cortex (PRC), which are specific regions of interest (ROIs) in AD pathogenesis. FreeSurfer automatically computes cortical reconstruction and volumetric segmentation, including segmentation of the subcortical white matter and deep gray matter volumetric structures ¹²⁸ and parcellation of the cortical surface ¹²⁹ according to a previously published parcellation scheme ¹³⁰. This labels cortical sulci and gyri, and thickness values are calculated in the ROIs.

Group comparisons of changes in regional volumes and thicknesses will be analyzed using a series of one-way analyses of variance (ANOVAs). The Scheffé post hoc procedure will be used to examine differences between means, and Pearson product—moment correlation coefficients will be used to evaluate the strength of relationships between changes in regional volumes and thicknesses and cognitive measures. Receiver operator curve analyses will determine sensitivity and specificity of various MTA cut-off points for distinguishing between diagnostic groups. Hazard ratios (HRs) for specific predictors of MTA progression and regression will be calculated using a three-state Markov model in continuous time. The proportional intensity model will be used to analyze effects of covariates on HRs.

To assess the effect of sargramostim treatment, as compared to placebo, on AD related changes in blood brain barrier permeability in individuals with mild-to-moderate AD.

CSF may be collected during screening, and at the EOT visit (i.e. within 2-10 days following the final treatment article injection) for a subset of participants for entry into the study or as part of an optional substudy. A venipuncture blood draw will be performed at each LP procedure visit to obtain serum. Albumin levels will be quantitated within CSF (in mg/dL) and serum (in g/dL) to calculate an Albumin Index (AI). Because albumin is neither synthesized nor metabolized intrathecally, albumin that is found within CSF that is free of blood contamination indicates that the albumin must have come from the plasma through the blood brain barrier (BBB). An AI value < 9 indicates an intact BBB, values 9-14 as slight impairment, values 14-30 as moderate impairment, values 30-100 as severe impairment, and values > 100 as complete breakdown of the BBB 72 . The BBB is known to be impaired in AD $^{131-133}$, and cerebral amyloid angiopathy (CAA), characterized by A β deposition on vessel walls, has been found in over 90% of AD cases 134 . In immunotherapy trials targeting amyloid in the parenchyma and cerebral vascular, the removal of pre-existing vascular amyloid has been attributed to onset of ARIA events (i.e. vasogenic edema and microhemorrhage) 135 , and while we and others have found GM-CSF to quickly reduce

amyloid in transgenic AD models ^{1,68}, no incidences of ARIAs have been observed in the current ongoing sargramostim-AD trial (NCT01409915). GM-CSF is known to induce angiogenesis and restore cerebral blood flow following experimental stroke ^{23, 24, 27, 28}. However, if sargramostim does indeed cause reductions in amyloid deposition over 24 weeks of administration in mild-to-moderate AD participants, evaluating treatment effects on BBB permeability in correlation with MRI safety measures is warranted. Thus, AI values will be calculated at screening and at EOT to assess any treatment-related changes in BBB permeability and to correlate values with any potential trial emergent ARIA events.

To assess the effect of sargramostim treatment, as compared to placebo, on AD-related changes in microstructural white matter measures in individuals with mild-to-moderate AD.

Numerous neuroimaging studies have shown that white matter (WM) tracts are associated with cognitive function, and that microstructural abnormalities are found in AD and other neurodegenerative diseases, as determined from high-resolution MRI diffusion tensor imaging (DTI) techniques ⁷³⁻⁷⁷. DTI metrics have been proposed as sensitive biomarkers for disease progression over short periods of time ⁷⁸, which makes it useful for assessing any WM changes in response to treatments, and specific DTI patterns have been shown to help distinguish between AD and other comorbid neurodegenerative diseases ^{79, 80}, to correlate with AD-related verbal fluency impairments ⁸¹, and with using neurite orientation dispersion and density imaging (NODDI) sequences of DTI, changes in neurite density can be approximated ^{82, 83}. Because GM-CSF has been shown to be a growth factor for oligodendrocytes ¹¹⁶, induce oligodendrocyte progenitor cells concurrent with amelioration of experimental spinal cord injury ^{34, 117}, and increase synaptic area concurrent with reversing cognitive impairment and pathology in transgenic AD models ^{1, 68}, high-resolution MRI with DTI and NODDI sequences will be performed at screening, weeks 3, 12, 18, EOT and metrics of DTI (e.g. FA, MD, NDI, ODI, etc.) will be monitored for any treatment-related changes.

To assess the effect of sargramostim treatment, as compared to placebo, on changes in sleep-related measures in individuals with mild-to-moderate AD.

Changes in quality of sleep have been long reported in onset and progression of AD ⁸⁴⁻⁸⁶, and decreases in non-rapid eye movement (NREM) slow wave activity (SWA) is known to be associated with Aβ deposition ⁸⁷. Our preclinical work and others have revealed that GM-CSF quickly removes amyloid in AD models ^{1,68}, of which it is not known whether quality of sleep improves with reductions in amyloid. For assessing any changes in qualitative measures of sleep in the participants, two sleep assessments (i.e. ISI, and PSQI) will be administered to both them and their study partner/caregivers at baseline, week 12, EOT, and at follow-up (45 days post-treatment) visits to assess quality of sleep measures and any changes that may occur throughout the trial. Mechanistically, melatonin and its signaling have been shown to be decreased in AD progression ⁸⁸⁻⁹², and GM-CSF has also been reported to increase melatonin secretion in preclinical studies ⁹³. Melatonin is made and secreted by the pineal gland, and calcification of the pineal gland increases with AD progression ⁹⁴⁻⁹⁷. High-resolution MRI scans, using susceptibility weighted imaging (SWI) sequence, will be performed at screening, weeks 3, 12, 18, EOT, and at follow-up (45 days post-treatment) to assess changes in pineal calcification measurements.

To assess the effect of sargramostim treatment, as compared to placebo, on changes in speech measures in individuals with mild-to-moderate AD.

AD is known to adversely impact temporal characteristics of spontaneous speech, such as speech tempo, number of pauses in speech, and their length, with speech alterations often noticed years before other cognitive deficits become apparent ^{98, 99}. Among the neuropsychological measures frequently used to assess semantic memory impairment in AD are verbal fluency tests, or speeded word-list generation, which consists of two types: phonemic (letter) fluency tests and category fluency tests. Fluency performance involves multiple brain processes and regions that are adversely impacted by AD pathology, and both phonemic and category fluency performances reveal declines in AD ^{100, 101}. Word retrieval in connected speech is also impaired in AD, and by using picture naming and picture descriptions, the total word output, percentages of content words, percentages of nouns, and percentages of pronouns out of all

words, type-token ratio of all words and type-token ratio of nouns alone, mean frequency of all words and mean frequency of nouns alone, and mean word length can be analyzed ¹⁰². A study participant interview will be given at baseline, week 12, EOT, and at follow-up (45 days post-treatment) visits to assess changes in speech fluency and word retrieval measures.

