To assess the effect of sargramostim treatment, as compared to placebo, on AD related changes in blood-brain barrier permeability in individuals with mild-to-moderate AD.	CSF will be collected from participants choosing CSF as confirmation for inclusion, or as an optional substudy, during screening, and at the EOT visit. A venipuncture blood draw will be performed at the same visit of each LP procedures to obtain serum. Albumin levels will be quantitated within CSF (in mg/dL) and serum (in g/dL) to calculate an Albumin Index (AI). Because albumin is neither synthesized nor metabolized intrathecally, albumin that is found within CSF that is free of blood contamination indicates that the albumin must have come from the plasma through the blood-brain barrier (BBB). An AI value < 9 indicates an intact BBB, values 9-14 as slight impairment, values 14-30 as moderate impairment, values 30-100 as severe impairment, and values > 100 as complete breakdown of the BBB ⁷² . AI values will be calculated at screening and at EOT visit to assess any treatment-related changes in BBB permeability and to correlate values with any potential trial emergent ARIA events.
To assess the effect that ApoE genotype may have upon predicting sargramostim treatment outcomes in individuals with mild-to-moderate AD.	ApoE genotyping will be performed using blood samples collected at Baseline visit of this trial for each participant. ApoE genotype will be determined by UC Health lab using established methods. Outcomes in the context of ApoE genotype will be compared. The genetic testing will be carried out at the end of the trial from stored blood, and participants will not be notified of any genetic testing results.
To assess the effect of sargramostim treatment, as compared to placebo, on inhibiting MTA in individuals with mild-to-moderate AD.	Atrophy in the entorhinal cortex (ERC), parahippocampal gyrus, and hippocampus (HPC), measured on high-resolution MRI scans, predict future cognitive decline and conversion to AD among individuals with mild cognitive impairment (MCI). Severity of MTA, assessed with high-resolution MRI scans, is strongly associated with severity of medial temporal lobe degenerative pathology, especially the severity of neurofibrillary pathology at autopsy. High-resolution MRI scans will be performed at screening, EOT visit, (and among participants in the optional amyloid PET procedure, at follow-up (45 days post-treatment)).

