5.4 Double Blind Treatment Period (Baseline Visit through Visit 24)

The treatment period is double-blinded, beginning at the Baseline Visit. At the Baseline Visit, appointments for all remaining visits should be made and scheduled as close as possible to the targeted date, based on the Baseline Visit. Visits done outside the allowable window will be considered a protocol deviation. Participants who meet the entry criteria for the clinical trial will be enrolled, randomized, and receive 24 weeks of treatment with either sargramostim or placebo.

The participant will follow the schedule of 7 days (Sunday through Saturday) of subcutaneous injection (178.57 µg/m²/day sargramostim or placebo) over the course of 24 weeks, for a total maximum of 168

treatment days. The first injection will be administered at the time of baseline (randomization) visit in the site's designated facility. The participant and study partner will receive training and a schedule on how to administer additional doses at home. For the first 3 weeks, the participant will receive a weekly dose administered by their caregiver with observation by a study nurse for correct injection technique. After the first 3 weeks, the injection will be observed by a study nurse at in-person visits at the site (Wk 6, Wk 12, Wk 18). Ongoing injection technique education will be provided as needed. If the caregiver is unable to administer the in-person visit injection, the injection will instead be administered by a trained medical professional. The investigational product will be distributed weekly to the participant either at their inperson clinic visit (Baseline, week 6, week 12, week 18) or at-home visit for subsequent subcutaneous injection at home, along with a new injection diary. An empty sharps container will be provided at the baseline visit and be replaced as needed for participants/caregivers to place used syringes into at home.

At the weekly double-blind treatment period site visits (Visit 2- through Visit 24), delegated study personnel will review and record changes to conmeds, adverse events, compliance and vital signs. As well, qualified staff will review inject sites to assess for possible adverse reactions.

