5.4.2.3 Double-Blind Treatment Imaging

High-resolution MRI scans will be completed at Visit 6, Visit 12, Visit 18 and EOT Visit.

In addition to the baseline FDG PET Scan, an End of Treatment FDG PET Scan will be completed at EOT Visit.

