Brain MRI scans will be obtained on a 3.0-tesla MRI machine using proprietary three-dimensional magnetization-prepared rapid-acquisition gradient echo or the three-dimensional spoiled gradient recalled echo sequences; MRI scans will be acquired with isotropic resolution, and contiguous slices with thickness of 1.5 mm or less will be reconstructed. Multiple MRI scans without contrast are safe as they do not involve exposure to radiation. Some individuals may have difficulty lying motionless during the scan or may experience anxiety while in the scanner. These issues can be mitigated by administering a sedative, prescribed by the study physician(s), prior to scanning. If necessary for the procedure, prescription/use of the prescription (e.g. lorazepam) will be documented by the study team, and the study will reimburse the participant for the cost of the prescription. If such a prescribed drug is used in the conduct of an MRI, the participant will need a driver (friend or family) to provide transportation for the visit. As well, any risks associated with the administration or use will be described to the study participant.

Brain MRI scans will be performed in Building 400 in the BIC or in Biosciences 3 on the CU-AMC campus, which is part of the AMC's comprehensive CU-Research Imaging Center. A separate Radiologist, blinded to participant identity and test article group, will examine each MRI scan for any evidence of ARIAs (i.e. vasogenic edema and microhemorrhage), and results, including any incidental findings, will be reported to the Study Coordinator and Study Physician. Another Radiologist or designate, also blinded to participant identity and test article group, will perform the FreeSurfer analyses.

Brain MRIs will be conducted at the Screening Visit, and Visit 6, 12, 18, EOT and, for individuals participating in the optional amyloid PET, at Follow-up.

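### The exploratory medial temporal atrophy comparison is fixed as unadjusted one-way ANOVA on change, names two of five scans for the endpoint, and adds a redundant Scheffé step and a Markov model that about 42 participants are very unlikely to support

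*Protocol*

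**What the plan says.** Protocol section 9.2.3, under the MTA objective, sets out the analysis in committed wording:

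- Group comparison: "Group comparisons of changes in regional volumes and thicknesses will be analyzed using a series of one-way analyses of variance (ANOVAs".
- Post hoc step: "The Scheffé post hoc procedure will be used to examine differences between means".
- Hazard ratios for predictors of MTA progression and regression: these "will be calculated using a three-state Markov model in continuous time", with a proportional intensity model for covariates. The three states are not defined.

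No baseline covariate, interval term or annualisation is named.

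The scans are described in several places. For the MTA endpoint, section 4.5 says: "High-resolution MRI scans will be performed at screening, EOT visit, (and among participants in the optional amyloid PET procedure, at follow-up". Section 5.4.2.3 says: "High-resolution MRI scans will be completed at Visit 6, Visit 12, Visit 18 and EOT Visit". Section 8.3.2 agrees: "Brain MRIs will be conducted at the Screening Visit, and Visit 6, 12, 18, EOT".

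Section 9.3 lists longitudinal regression only among additional tests that may be used. Section 9.3.1 leaves a full SAP for later.

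**The concern.** Atrophy accumulates with time, so a change score depends partly on how long the participant was observed. The pre-treatment scan is the screening MRI, which may be many weeks before the first dose, and the EOT scan can move later or earlier. A one-way ANOVA on change treats all these intervals as equal and does not use the screening volume as a covariate.

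Section 4.5 ties MTA to the two end scans although three intermediate high-resolution scans are scheduled for every participant. In a trial of 42, split 28:14, that is information already paid for.

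The other two elements do not suit the design. Scheffé is meant for several groups, and there are two arms. A multistate model for progression and regression needs repeated observed moves between defined states, and a 24-week trial of this size will produce few.

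**Working it through.** The protocol gives no sample size, SD or power for MTA, so there is no planned figure to reproduce. Rates, SDs and correlations below are assumptions, shown as ranges.

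**1. Time between screening and EOT scans.** Inputs:
- screening to baseline, at most 84 days (section 2, screening footnote 1);
- treatment "over the course of 24 weeks, for a total maximum of 168" days (section 5.4);
- EOT 2 to 10 days after the last dose (section 2);
- an elective pause of up to 28 days, added to the treatment period (section 7.5.1).

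| Case (completers) | Shortest | Longest | Ratio |
|---|---|---|---|
| No pause | 0+168+2 = 170 | 84+168+10 = 262 | 1.54 |
| With pause | 170 | 262+28 = 290 | 1.71 |
| With pause, screening scan no later than week −1 | 7+168+2 = 177 | 290 | 1.64 |
| No pause, scan no later than week −1 | 177 | 262 | 1.48 |

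Two provisions widen this. Section 6.3 lets an MRI up to two months old be reused at rescreening (290+60 = 350 days). Section 6.4.1 brings EOT assessments forward as an Early Termination Visit, so the interval can fall well below 170 days.

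**2. Cost of ignoring the interval.** Added variance as a share of Var(change) = (rate × SD of interval)² / SD(change)². Assume intervals uniform over 170–290 days: SD = 120/√12 = 34.6 days = 0.095 years.
- Loss 2%/year, SD of change 3%: (2×0.095)²/3² = 0.4%.
- Loss 4%/year, SD 2%: (4×0.095)²/2² = 3.6%.
- Loss 6%/year, SD 1.5%: (6×0.095)²/1.5² = 14%.

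If the mean interval differed between arms by 28 days, the contrast would shift by 4 × 28/365.25 = 0.31 percentage points at 4%/year.

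**3. Baseline adjustment.** With equal variances and correlation ρ, Var(change) = 2σ²(1−ρ) and Var(ANCOVA) = σ²(1−ρ²), so the ratio is (1+ρ)/2: 0.75 at ρ = 0.5, 0.95 at 0.9, 0.975 at 0.95, 0.995 at 0.99.

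**4. Five scans against two.** The measurement-error variance of a participant's slope is proportional to 1/Σ(t − mean t)². Scans are at −x, 6, 12, 18 and 25 weeks.
- x = 0: five-scan sum 384.8, two-scan sum 25²/2 = 312.5, ratio 0.81.
- x = 12: 792.8 and 37²/2 = 684.5, ratio 0.86. At x = 8 it is also 0.86.

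That is 14–19% lower, for measurement error only. Adding a between-person slope SD of 1–3%/year to a measurement SD of 1–3% (first scan 42 days before dose) gives ratios of 0.86 to 0.94, a gain of 6–14%. These figures are for a slope through all scans. They indicate the value of the extra scans but are not the exact gain of the model proposed below.

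**5. Scheffé.** With k = 2 its critical value is (k−1)F(1,40) = 4.085 = t²(40), identical to the ANOVA F test.

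**6. Markov model.** Simulation of three ordered states with moves between neighbours, 28:14, 4,000 runs. Assumed progression is 0.2–0.8/year, regression 0.05–0.3/year, hazard ratio 0.7.

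| | Two scans | Five scans |
|---|---|---|
| Mean progressions, active / placebo | 1.5–4.9 / 1.1–3.3 | 1.6–5.7 / 1.1–3.9 |
| Mean regressions, active / placebo | 0.5–2.5 / 0.3–1.2 | 0.6–3.2 / 0.3–1.6 |
| At least one neighbouring transition empty in an arm | 97–100% of runs | 88–100% |
| No regression at all on placebo | 30–76% | 20–76% |

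**The case against.** The strongest reply is that much of this belongs in the SAP. Section 9.2.3 refers to changes without excluding annualisation, section 4.5 does not say that only two scans will be used, and section 8.3.2 sends scans for FreeSurfer analysis without limiting the visits. This stands in part. A reader might infer that the protocol orders the intermediate scans to be discarded, but it does not. It names two scans for MTA and is silent on the rest. What remains is that ANOVA, Scheffé and the Markov model are stated as what will be done, and longitudinal regression is only optional.

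Second, randomisation keeps the unadjusted comparison unbiased if intervals are balanced. That is correct, so a reader should not infer that the planned ANOVA is biased as it stands. Bias needs pauses or early termination to differ by arm, which is possible but not shown. The 0.31-point shift is conditional on such a difference.

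Third, the 170-day minimum puts the screening MRI on the day of first dose, which the tiered screening in section 5.3.1 makes unrealistic. The same applies to the 19% gain. Both are limits, not typical values.

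Fourth, a reader might infer that each participant gives one transition, that the Markov model cannot be estimated, and that it cannot address treatment. None of these is established. Amyloid PET participants also have a follow-up MRI (section 5.5), the states are undefined so the parameter count is open, and arm could be a covariate. The simulation shows only that sparse or empty transitions are very likely under the assumed rates and structure.

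**Conclusion.** The point holds as one of efficiency and fit. Section 9.2.3 fixes an unadjusted comparison of change when scan intervals can differ about 1.5- to 1.7-fold among completers. The endpoint text leaves three scheduled scans unnamed. Scheffé is redundant but harmless. The Markov model is very unlikely to give stable hazard ratios from about 42 participants with few scans each.

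The expected gain from repair is modest: 14–19% lower slope variance for measurement error alone, 6–14% with between-person slope variation, and 2.5% or less from the baseline covariate if scans correlate at 0.95 or above. The interval term matters more if atrophy is fast and measurement precise (0.4% to 14% added variance). All these sizes rest on assumed rates, SDs and correlations.

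It does not follow that the MTA objective cannot be answered. It is one of several exploratory objectives, and the primary safety and secondary MMSE conclusions are untouched. The change is worth making because it is cheap, and it should be settled before unblinding.

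**What to change.** In section 9.2.3, replace the ANOVA and Scheffé sentences with one model per region: a linear mixed model of volume or thickness at the post-baseline scans (weeks 6, 12, 18, and EOT or early termination), at actual time since first dose. Include arm, time and arm-by-time, with the screening value and the screening-scan-to-first-dose interval as covariates. The effect is the arm difference at week 24.

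The screening scan should not also be an outcome. That would use it twice and put up to 84 pre-dose days on the treated slope.

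If only two scans are used, apply ANCOVA to the EOT value with the screening value and the pre-dose screening interval as covariates. The post-dose part of the interval should not be a covariate, because pauses and early termination occur after randomisation and may depend on arm.

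Delete the three-state Markov and proportional intensity sentences. In section 4.5, list the week 6, 12 and 18 scans for MTA so that the endpoint and the analysis agree.

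The cost is analysis wording plus at most 3 × 42 = 126 additional FreeSurfer runs on scans already scheduled. This assumes those visits include the three-dimensional sequence, which section 8.3.2 describes for brain MRI without limiting it to particular visits. No new procedures are needed.
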